7.3.4 Interim analyses

In accordance with local regulation for NIS studies, interim analyses are planned biannually for the initial two years and annually thereafter.

7.4 HANDLING OF MISSING DATA

As this is non-interventional study, there are no required investigations and diagnostic procedures (e.g. lab, ultrasound).

Maximum attempt will be made to ensure the completeness of data collection. All available data will be used in the data analysis. There will be no imputation of data to fill the missing values.

7.5. RANDOMISATION

This section is not applicable as this is a non-interventional study.

7.6 DETERMINATION OF SAMPLE SIZE

Sample size of 3,000 patients is based on the requirement of the local regulatory authority (Korean FDA). The number of patients enrolled for short-term surveillance will be 1,500 and for long-term follow up 1,500. As per regulation, long-term surveillance is necessary for the indication. It will be conducted to 50% of total number of enrolled patients.

Proprietary confidential information. © 2014 Boehringer Ingelheim International GmbH or one or more of its affiliated companies.

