5.1.2 Assessment of effectiveness

Since the patient follow-up period is only 12 weeks (in case of long-term FU, 24 weeks), it is not possible to perform any meaningful effectiveness assessment of Pradaxa in this NIS. However, since it is a requirement to evaluate also effectiveness in all regulatory requisite NIS in Korea and as requested by **MFDS**, a descriptive analysis of effectiveness endpoint will be performed.

Effectiveness analysis will be performed to the patients who have been on Pradaxa more than 12 weeks (in case of long-term FU, 24 weeks).

The following definitions apply and should be used as a guide when reporting a thrombotic event:

Stroke:

Stroke is an acute onset of a focal neurological deficit of presumed vascular origin lasting for 24 hours or more or resulting in death. The stroke is categorized as ischemic or hemorrhagic or uncertain classification (based on CT or MR scanning or autopsy). Fatal stroke is defined as death from any cause within 30 days of stroke. Severity of stroke will be assessed by modified Rankin Scale (see Table 10.1:4) at discharge from hospital and/or at 3-6 months later (if available).

Systemic embolism:

Systemic embolism is an acute vascular occlusion of the extremities or any organ (kidneys, mesenteric arteries, spleen, retina or grafts), typically documented by angiography, surgery, scintigraphy, or autopsy.

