6.2.2 Treatment period(s)

As per regulations, enrolled patients will be followed up for a 12 week or 24 week treatment period. There will be a visit window of ± 2 weeks. To minimize the selection bias at the site level, the goal is to have participating centers reflect a balance between general hospitals and clinics for short-term or long-term surveillances.

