6.2.2.2 Visit 2 (12 \pm 2 weeks from Visit 1)

After 12 \pm 2 weeks from Visit 1, the patients will return for follow-up. The followings will be noted and recorded in the eCRF:

Proprietary confidential information. © 2014 Boehringer Ingelheim International GmbH or one or more of its affiliated companies.

- Visit date
- Any change of Pradaxa dose given
- Any changes in laboratory tests which required actions on drug dosage since last visit or any laboratory values performed to monitor the increased risk of bleeding ie. aPTT
- Vital signs: average blood pressure (sitting arm) and pulse rate
- Effectiveness endpoints: incidence of stroke or systemic embolism
- Anti-thrombotic therapy: any change in the anti-thrombotic therapies since last visit (excluding Pradaxa)
- Concomitant medications including new medications taken since last visit: any change in the concomitant medications (dose and dosing intervals)
- Any adverse events noted
- Treatment compliance
- **Study completion status: for the prematurely withdrawn patients, this section should be recorded to assess the safety information and the reason for withdrawal**
- NIS physician's electronic signature for data integrity (do not record this section for long-term FU cases)

At Visit 2, the patients on long-term follow-up will be reminded to contact the NIS physician in the event of any adverse events noted hereafter.

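### No rule says how or when a patient becomes a 24-week case, so persistence-based selection is not excluded; separately, the effectiveness set drops early stoppers under any allocation

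*Combined protocol and SAP*

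**What the plan says.** Section 7.6 takes the total from the regulator ("Sample size of 3,000 patients is based on the requirement of the local regulatory authority (Korean FDA") and divides it: "The number of patients enrolled for short-term surveillance will be 1,500 and for long-term follow up 1,500". Of the longer surveillance it adds: "It will be conducted to 50% of total number of enrolled patients". Section 6.2.2 states that "enrolled patients will be followed up for a 12 week or 24 week treatment period", with a window of two weeks either side.

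On who goes where, the nearest text is also in section 6.2.2: "To minimize the selection bias at the site level, the goal is to have participating centers reflect a balance between general hospitals and clinics". That sentence goes on to name the two surveillances. Section 3.3 calls for consecutive enrolment at each site, and section 7.5 marks randomisation as not applicable. Neither the Visit 1 list (section 6.2.2.1) nor the baseline column of the flow chart includes a follow-up cohort.

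At Visit 2 (section 6.2.2.2) the cohorts part. The final item is "NIS physician's electronic signature for data integrity (do not record this section for long-term FU cases"), and long-term patients are reminded to report later adverse events. Visit 3 (section 6.2.2.3) is for long-term cases only.

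The label then feeds the analysis. Section 5.1.2 says: "Effectiveness analysis will be performed to the patients who have been on Pradaxa more than 12 weeks (in case of long-term FU, 24 weeks"). Section 5.2.2.2 collects adverse events until 7 days after the last follow-up visit. Section 7.3.3 bases safety on all treated patients, without reference to cohort.

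**The concern.** The split is fixed in number but not in membership. If a patient can be designated long-term once the first 12 weeks are known, membership can depend on how those weeks went. Patients still on drug and doing well would tend to fill the 24-week cohort, and early stoppers would collect in the 12-week cohort.

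This bears on the primary objective, which is safety. Once short-term patients have left observation, all new safety information comes from long-term cases. If those are selected persisters, the later safety profile is that of patients who had already tolerated the drug, and no analysis can recover what was not observed in the others. Effectiveness results reported by cohort would be affected in the same way.

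A second problem sits beside this one. The effectiveness set is conditional on staying on drug past a threshold. Read literally, a patient who stops before it is left out, even if the reason for stopping was a stroke, which is the endpoint itself.

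**Working it through.** **1. The plan's figure.** 0.50 × 3,000 = 1,500, which matches section 7.6. There is no power calculation to reproduce.

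**2. Is there a designation rule?** Consecutive enrolment governs entry to the study, not cohort. The balance goal in section 6.2.2 concerns types of centre and gives no rule for patients within a centre. The baseline lists contain no cohort item. The earliest per-patient procedures that differ by cohort are the sign-off and the reminder at Visit 2. So no rule or time point appears in the text supplied.

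**3. Who supplies the later safety data?** A short-term patient's last visit is at week 12 ± 2. Adding 7 days, new events are collected until about week 13, or week 12 + 2 + 1 = 15 at the latest. Section 6.2.3 extends follow-up only for events already noted. After that, new events can come only from long-term cases.

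**4. Worst-case size.** Let d be the share of all 3,000 patients who stop by week 12. The documents give no value, so d is assumed. If all 1,500 long-term patients are persisters, all 3,000d stoppers fall among the 1,500 short-term patients, a share of 3,000d / 1,500 = 2d.

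| Assumed d | Stoppers | Long-term cohort | Short-term cohort |
|---|---|---|---|
| 10% | 300 | 0% | 300/1,500 = 20% |
| 20% | 600 | 0% | 600/1,500 = 40% |
| 30% | 900 | 0% | 900/1,500 = 60% |

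**5. A milder case.** Take d = 20%. Suppose 750 long-term patients are designated at enrolment regardless of outcome (0.20 × 750 = 150 expected stoppers) and the other 750 are taken later from persisters (none). Early stopping is then 150/1,500 = 10% long-term and (600 − 150)/1,500 = 30% short-term.

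**6. Benchmark.** With outcome-independent designation the expected gap is zero, with 95% chance variation of 1.96 × √(2d(1 − d)/1,500). At d = 20% this is 1.96 × √(0.32/1,500) = 1.96 × 0.0146 = 0.029, or ±2.9 percentage points. At d = 30% it is ±3.3 points.

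**7. Effect on event risk.** Assume 12-week risks of 10% in persisters and 20% in stoppers, with d = 20%. Overall risk is 0.8 × 10% + 0.2 × 20% = 12%. In the worst case the long-term cohort shows 10% and the short-term cohort 0.6 × 10% + 0.4 × 20% = 14%. If the stoppers' risk is 40%, the figures are 16% overall, 10% and 22%. In both examples the average of the two equal-sized cohorts returns the overall risk, so pooled 12-week safety is unaffected.

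**8. The effectiveness set.** The thresholds in section 5.1.2 apply however patients were designated, so perfect allocation at Visit 1 would not bring early stoppers back. Section 7.3.1 speaks of treated patients and does not repeat the thresholds, so the two sections also need to be aligned.

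**The case against.** The strongest reply is that late designation is read into silence. Section 7.6 speaks of patients enrolled for one surveillance or the other, and the Visit 2 reminder treats long-term patients as already known. The balance sentence in section 6.2.2 could even mean that centres, not patients, are divided between the surveillances, in which case choice within a site would not arise. The eCRF (Attachment 1) and the TSAP, to which section 7 refers for details, are not in the file and may hold a rule. This stands in part: it makes early designation plausible, but none of the wording states a rule or a time. A rule found only in an analysis plan would not undo a choice made at the site.

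It can also be said that the study is descriptive, lists no short-versus-long comparison, bases safety on all treated patients, and concedes in section 5.1.2 that effectiveness cannot be meaningfully assessed. Withdrawals are recorded at Visits 2 and 3, and section 7.3.3 has patients lost to follow-up characterised. These points limit the harm but leave the later safety data exposed. A descriptive incidence still needs a defined population.

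A reader might infer that physicians may choose the cohort at any time, or that the omitted Visit 2 sign-off is the only mark of a long-term case. The documents support neither: no text grants that choice, and the reminder and the Visit 3 heading are also marks. Nor does a patient stopping at week 16 demonstrate selection. A short-term patient's final visit falls by week 14, and a long-term patient's exclusion follows from section 5.1.2 under any allocation.

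**Conclusion.** The point holds as a gap that permits selection, not as evidence that selection is planned or has occurred. What is exposed is safety information from roughly weeks 12 to 24 and the cohort-specific effectiveness results. It would be wrong to conclude that the overall safety results are biased.

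The 0% against 20%, 40% or 60% contrast is an upper bound. It rests on assumed stopping rates of 10% to 30% and on every long-term patient being a persister. Partial selection at 20% stopping still gives a 20-point gap (10% against 30%), well beyond the ±2.9 points expected by chance.

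The restriction in section 5.1.2 is a separate defect and does not depend on how cohorts are formed. Both should be corrected.

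**What to change.** - For patients enrolled from now on, record and lock the follow-up cohort in the eCRF at Visit 1 under a rule that cannot depend on outcome: consecutive order within site, a system-generated list, or sites designated in advance. State the rule in sections 6.2.2 and 7.6.
- For patients already enrolled, report when and how each was designated. Section 3.1 expected enrolment to begin in 2012 and this version is dated June 2013, so such patients are likely.
- Replace the restriction in section 5.1.2 so that every treated patient is analysed in the assigned cohort, including those who stop or are lost, using observed follow-up time. Bring section 7.3.1 into line.
- Use weeks 0-12 from both cohorts together for all 12-week results.

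The cost is one locked field, a few protocol sentences and a revised analysis set. The 1,500/1,500 split stays, and only length of observation is assigned, so prescribing remains with the physician. The drawbacks are that sites lose freedom to choose patients for longer follow-up, and patients already enrolled cannot be reassigned. If the unsupplied eCRF already fixes the cohort at Visit 1 by such a rule, the first item reduces to stating it in the protocol.

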8. DATA PROTECTION, STUDY RECORDS

The International Conference on Harmonization/Harmonized Tripartite Guideline for Good Clinical Practice (ICH/GCP) does not often apply to NIS studies as most elements are relevant for controlled clinical trials. However, in this NIS study, all attempts will be made to adhere, as close as possible, to the standards of ICH/GCP.

The protocol of this regulatory requisite NIS study will be submitted to the Ministry of Food and Drug Safety (MFDS) for notification. It is not a local requirement in Korea to obtain Institutional Review Board (IRB) approval for the conduct of regulatory requisite NIS studies. However, the protocol of this NIS study will be submitted to IRBs whenever required or requested by these institutions. This study will be conducted in accordance with the Standards for Re-examination of New Medicines notified by MFDS, Korean Pharmaceutical Affairs Code (KPAC), Enforcement Regulation of KPAC and other applicable local laws and industry code (including but not limited to the Regulations on Fair Competition in the Trade of Medicines of KPMA and KRPIA).

Boehringer Ingelheim Korea will submit periodic reports during re-examination period, and the final report to MFDS upon study completion. The periodic report for the final year will be substituted with the final report. When required, the interim reports and the final report will be submitted to the IRBs as well.

8.1 STUDY APPROVAL, PATIENT INFORMATION, AND INFORMED CONSENT

This study will be initiated only after all required legal documentation has been reviewed and approved by the respective IRB/IEC and the competent authority (CA) according to the local regulations. The same applies for the implementation of changes introduced by amendments.

Prior to patient participation in the study, written data release consent shall be obtained from each patient (or the patient's legally accepted representative). Each signature must be personally dated by each signatory and the data release consent and any additional patient-information form retained by the NIS physician as part of the trial records. A signed copy of the data release consent and any additional patient information must be given to each patient or the patient's legally accepted representative.

The patient must be informed that his/her personal study-related data will be used by Boehringer Ingelheim Korea in accordance with the local data protection law. The level of disclosure shall also be explained to the patient.

The patient shall be informed that his/her medical records may be examined by authorised monitors (NIS Managers) or Clinical Quality Assurance auditors appointed by sponsor, by appropriate IRB/IEC members, and by inspectors from regulatory authorities.

Proprietary confidential information. © 2014 Boehringer Ingelheim International GmbH or one or more of its affiliated companies.

8.2 DATA QUALITY ASSURANCE

A quality assurance audit/inspection of this study may be conducted by the sponsor or sponsor's designees or by IRBs/IECs or by regulatory authorities. The quality assurance auditor will have access to all medical records, the participating physician's study-related files and correspondence, and the data release agreement documentation of this study.

8.3 RECORDS

All of the clinical data will be captured via a web-based EDC (Electronic Data Capture) System. The site staff will enter and edit the data via a secure network, with secure access features (username, password and secure identification – an electronic password system). A complete electronic audit trail will be maintained. The treating physician will approve the data using an electronic signature.

Patients will not be identified on the eCRF by name. Appropriate coded identification (i.e., patient number) will be used. The treating physician will make a separate confidential record of these details (patient identification code list) to permit identification of all patients enrolled in this study in case follow-up is required. Likewise, any supporting documentation will be redacted of any patient identifying information, and the patient ID number clearly written on the documents.

8.3.1 Source documents

Source documents provide evidence for the existence of the patient and substantiate the integrity of the data collected. Source documents will be filed at the treating physician's site.

It is necessary that the data entered in the eCRFs that are transcribed from the source documents are consistent with the source documents or the discrepancies need to be explained. The treating physician may need to request previous medical records, transfer records, and current medical records.

8.3.2 Direct access to source data and documents

The NIS physician / site will permit study-related monitoring, audits and regulatory inspection, providing direct access to all related source data/documents. All source documents including eCRFs will be made available for review by sponsor's Medical Project Manager (MPM) or designees and inspection by health authorities (e.g., MFDS). The MPM and auditor may review all eCRFs, and written data release agreements. The accuracy of the data will be verified by reviewing the documents described in Section 8.3.1.

8.3.3 Storage of records

The NIS physician and the site are jointly responsible for maintaining essential study documents for 3 years after completion of the study (defined as termination date of re-examination period) by the Pharmaceutical Affairs Law and shall take measures to prevent accidental or premature destruction of these documents.

Proprietary confidential information. © 2014 Boehringer Ingelheim International GmbH or one or more of its affiliated companies.

8.4 PROCEDURES FOR REPORTING ADVERSE EVENTS

8.4.1 Time windows

All AEs, serious and non-serious, occurring during the course of the rNIS will be collected, documented and reported to the sponsor by the investigator on the appropriate eCRF. Reporting will be done according to the specific definitions and instructions detailed in the 'Adverse Event Reporting' section of the site materials (that include all necessary documents, the protocol, instructions for conducting rNIS, the package insert etc.).

The investigator has the responsibility to report AEs during the specified observational phase.

Any SAE, whether or not considered related to Pradaxa capsules, must be reported immediately via eCRF and SAE Report Form.

8.4.2 Documentation of adverse events and patient narratives

Expedited reporting of serious adverse events, e.g. suspected unexpected serious adverse reactions (SUSARs) to health authorities and IECs/IRBs, will be done according to the local regulatory requirements.

For each AE, the investigator will provide the onset date, end date, intensity, outcome, seriousness and action taken with Pradaxa capsules. The investigator will determine the relationship of Pradaxa capsules to all AEs as defined in the 'Adverse Event Reporting' section of the protocol.

8.5 STATEMENT OF CONFIDENTIALITY

Individual patient medical information obtained as a result of this study will be considered confidential and disclosure to third parties will be prohibited with the exceptions noted below. Patient confidentiality will be ensured by using patient identification code numbers.

Treatment data will be made available to the patient's personal physician or to other appropriate medical personnel responsible for the patient's welfare. Data generated from the study will be made available for inspection on request by the participating physicians, the sponsor and/or its representatives and/or designees, by the IRBs/IECs and the regulatory authorities.

8.6 PUBLICATION POLICY

Boehringer Ingelheim, to the best of their ability will support the process of free exchange of relevant scientific information. Any publication of the result of this NIS study must be consistent with the Boehringer Ingelheim publication policy.

10. APPENDICES

10.1 RISK SCORES FOR AF PATIENTS

Data collected at the baseline visit will be used to generate the following scores for use in the respective analysis:

Table 10.1: 1 CHADS₂ Stroke Risk Score

CHADS₂ component	Points
Congestive heart failure	1
Hypertension	1
Age greater than 75 years	1
Diabetes mellitus	1
Prior cerebral ischemia (i.e., stroke, TIA)	2
Maximum score	6

CHADS₂ score is based on a point system in which 2 points are assigned for the history of stroke or transient ischemic attack and 1 point each for age more than 75 years, hypertension, diabetes, or clinical heart failure or impaired left ventricular systolic function (generally interpreted as an ejection fraction $\leq 40\%$). A CHADS₂ score of 0 identifies patients at low stroke risk, a score of 1 to 2 identifies patients at moderate stroke risk, and a score greater than 2 identifies patients at high stroke risk (P06-10925).

Table 10.1: 2 CHA₂DS₂-VASc Stroke Risk Score

CHA ₂ DS ₂ -VASc Stroke score	
Risk factors for stroke and thrombo-embolism in non-valvular AF	
Major risk factors	Clinically relevant non-major risk factors
Previous stroke, TIA, or systemic embolism Age \geq 75 years	Heart failure or moderate to severe LV systolic dysfunction (e.g. LV EF \leq 40 %) Hypertension - Diabetes mellitus Female sex - Age 65-74 years Vascular disease
Risk factor-based approach expressed as a point based scoring system, with the acronym CHA₂DS₂-VASc (Note: maximum score is 9 since age may contribute 0, 1, or 2 points)	
Risk factor	Score
Congestive heart failure/LV dysfunction	1
Hypertension	1
Age \geq 75	2
Diabetes mellitus	1
Stroke/TIA/systemic embolism	2
Vascular disease*	1
Age 65-74	1
Sex category (i.e. female sex)	1
Maximum score	9

* Myocardial infarction, complex aortic plaque and PAD

The CHA₂DS₂-VASc risk score is based on a point system in which 2 points are assigned for the history of stroke or TIA, or age \geq 75; and 1 point each for age 65–74 years, hypertension, diabetes, cardiac failure, vascular disease and female sex. On the basis of the risk strata defined in previous guidelines, a CHA₂DS₂-VASc score of 0 corresponds to “low risk”, a score of 1 corresponds to “intermediate risk”, and a score of 2 or more corresponds to “high risk” (R10-5332).

Table 10.1: 3 HAS-BLED Bleeding Risk Score

Clinical characteristics comprising the HAS-BLED bleeding risk score		
Letter	Clinical characteristics	Points awarded
H	Hypertension	1
A	Abnormal renal and liver function (1 point each)	1 or 2
S	Stroke	1
B	Bleeding	1
L	Labile INRs	1
E	Elderly (e.g. age > 65 years)	1
D	Drugs or alcohol (1 point each)	1 or 2
Maximum score		9

Hypertension is defined as systolic blood pressure >160 mmHg. 'Abnormal kidney function' is defined as the presence of chronic dialysis or renal transplantation or serum creatinine $\geq 200 \mu\text{mol/L}$. 'Abnormal liver function' is defined as chronic hepatic disease (e.g. cirrhosis) or biochemical evidence of significant hepatic derangement (e.g. bilirubin $> 2 \times$ upper limit of normal, in association with aspartate aminotransferase/alanine aminotransferase/alkaline phosphatase $> 3 \times$ upper limit normal). 'Bleeding' refers to previous bleeding history and/or predisposition to bleeding, e.g. bleeding diathesis, anemia, etc. 'Labile INRs' refers to unstable/high INRs or poor time in therapeutic range (e.g. $< 60\%$). Drugs/alcohol use refers to concomitant use of drugs, such as antiplatelet agents, non-steroidal anti-inflammatory drugs, or alcohol abuse, etc. If a patient is not on VKA the value for 'labile INRs' will not be assessed.

A HAS-BLED score of ≥ 3 indicates 'high risk' for AF patients to develop a bleed and some caution and regular review of the patient is needed following the initiation of antithrombotic therapy, whether with VKA or aspirin (R10-6394).

Table 10.1: 4 Modified Rankin Scale (mRS)

Definition of disabling stroke by modified Rankin Scale:

Grade 0: no symptoms at all

Grade 1: no significant disability despite symptoms;
able to carry out all usual duties and activities

Grade 2: slight disability:
unable to carry out all previous activities but able to look after own affairs
without assistance

Grade 3: moderate disability
requiring some help but able to walk without assistance

Grade 4: moderate severe disability
unable to walk without assistance and unable to attend to own bodily needs
without assistance

Grade 5: severe disability
bedridden, incontinent, and requiring constant nursing care and attention

Grade 6: dead

